7.2. Laboratory Procedures/Evaluations

7.2.1. Clinical Laboratory Evaluations

Clinical Chemistry, Hematology, Coagulation and Other assessments: Clinical chemistry assessed includes:

- Glucose
- Creatinine
- Total Protein
- Albumin
- Blood Urea Nitrogen
- AST/Serum Glutamic-Oxaloacetic Transaminase (SGOT)
- ALT/Serum Glutamic-Pyruvic Transaminase (SGPT)
- Alkaline Phosphatase (ALP)
- Total Bilirubin
- Na⁺
- K⁺
- Cl⁻
- Mg
- Ca⁺²
- PO₄
- CO₂

Hematology:

- Hemoglobin A1c (HbA1c; baseline measurement only)
- CBC

Coagulation:

- PT
- aPTT

Others:

- CA19-9
- β -HCG pregnancy test

Note: Renal function will be assessed utilizing the Cockcroft-Gault formula. CBC (complete blood count) and CMP (comprehensive metabolic panel) will be monitored weekly, on Day 1 and Day 7 or 8 (may be done \pm 1-2 days if falls on a weekend or holiday), for toxicity assessment of study drugs.

7.3. Study Schedule

7.3.1. Screening

7.3.1.1 **Screening Visit:** day: -28

7.3.1.2 **Informed Consent:** Obtain informed consent of potential participant verified by signature on written informed consent for screening form

7.3.1.3 **Medical History:** Review medical history to determine eligibility based on inclusion/exclusion criteria

7.3.1.4 **Medical Examinations:** Perform medical examinations needed to determine eligibility based on inclusion/exclusion criteria

Pre-Study Screening Tests & Pre-Study Safety Assessment:

Pre-Study Screening Tests:

Pre-study screening tests, which are also enrollment evaluations, must be performed according the following time frames:

- Within 4 weeks of randomization: tumor assessments (triphase contrast CT of the chest, abdomen and pelvis or MRI), and optional blood and serum samples.
- Within 2 weeks of randomization: medical history, physical exam, vital signs (including heart rate), height, weight, ECG, ECOG, Hemoglobin A1c, evaluation of symptoms and medications, clinical chemistry, hematology, CA19-9 and coagulation.
- Within 1 week of randomization: Serum pregnancy test for women of child-bearing potential.

Pre-Study Safety Assessment:

All safety assessment tests are performed during screening (performed within 2 weeks prior to treatment with devimistat) with results available from local labs for review within 24 hrs. before administration of the anti-tumor agents. These safety assessments include:

- Evaluation of symptoms
- Vital signs including heart rate
- ECOG performance status and survival
- Clinical chemistry
- NCCN-FACT FSHI-18 questionnaire (PRO)
- Renal function
- Hematology
- Coagulation (PT and aPTT)
- CA19-9

7.3.2. Enrollment/Baseline & Treatment Cycle Details

7.3.2.1 Enrollment/Baseline Visit: Cycle 1, Day 1

7.3.2.2 Administration of Study Treatment: Eligible subjects will be randomized to treatment following screening. The study site will obtain subject's identification and randomization to treatment arm from the IxRS.

CPI-613[®] (devimistat): 500 mg/m² of devimistat will be administered on days 1 and 3 of every 14 days (2 weeks) cycle (+/- 24 hours) at the rate of 4mL/min via a central venous catheter. Devimistat infusion must be administered concurrently with D5W at the rate of 125mL/hour (2.08mL/min) via a central venous catheter.

mFFX: mFFX will be administered on days 1, 2 and 3 of every 14 days (2 weeks cycle) using the regimen below via IV line.

- Oxaliplatin at 65 mg/m² given as a 2-hr IV infusion
- Folinic acid at 400 mg/m² given as a 90-min (1.5 hr) infusion immediately after oxaliplatin, and concurrently with irinotecan (Irinotecan at 140 mg/m² given as a 90-min IV infusion) via a Y-connector
- Flurouracil (5-FU) at 400 mg/m² as bolus followed by a 42-48-hr infusion at 2,400 mg/m², starting immediately after completion of folinic acid and irinotecan

FFX: FFX will be administered on days 1, 2 and 3 of every 14 days (2 weeks cycle +/- 24 hours) using the regimen below via IV line.

- Oxaliplatin at 85 mg/m² given as a 2-hr IV infusion
- Folinic acid at 400 mg/m² given as a 90-min (1.5 hr) infusion immediately after oxaliplatin, and concurrently with irinotecan (Irinotecan at 180 mg/m² given as a 90-min IV infusion) via a Y-connector
- Flurouracil (5-FU) at 400 mg/m² as bolus followed by a 42-48-hr infusion at 2,400 mg/m², starting immediately after completion of folinic acid and irinotecan

CYCLE: 1 (Day 1 – Day 14 +/- 24 hours):

Devimistat Arm1 (devimistat+mFFX)

Day 1:

I. Pre-dosing Tests:

- Evaluation of vital signs (including heart rate)*,
- ECOG performance status*,
- Survival*,
- Clinical chemistry*,
- Hematology*,
- Coagulation*,
- Triphase contrast CT of the chest, abdomen and pelvis **,
- CA19-9**,
- NCCN-FACT FSHI-18 questionnaire (if not collected during Screening) (also referred to as PRO is this protocol),
- Blood sampling for PK (see Full PK or Sparse PK sampling schedule in Section 7.1.1, Table 12 or Table 13),
- Blood sampling for Cardiac marker (Troponin I) (Please make certain that this test occurs no sooner than 30 minutes prior to dosing.),
- ECG measurement (see Full ECG or Sparse ECG measurement schedule in Section 7.1.1, Table 14 or Table 15)

- II. Devimistat 500 mg/m² infused at the rate of 4 mL/min concurrently with D5W at the rate of 125mL/hour (2.08mL/min) via a central venous catheter on days 1 and day 3 of each 14-day cycle of mFFX (given immediately after devimistat administration on Day 1) #:
- Oxaliplatin at 65 mg/m² given as a 2-hr IV infusion
 - Folinic acid at 400 mg/m² given as a 90-min (1.5 hr) IV infusion immediately after oxaliplatin
 - Irinotecan at 140 mg/m² given as a 90-min (1.5 hr) IV infusion via a Y- connector concurrently with Folinic acid
 - Flurouracil (5-FU) at 400 mg/m² as IV bolus followed by a 42-48-hr continuous IV infusion at 2,400 mg/m², starting immediately after completion of folinic acid and irinotecan

Note:

**These tests are performed in local labs with results available for review within 24 hrs. before administration of the anti-tumor agents.*

*** Performed at the end of every 4th cycle.*

**Dosing of agents in the mFFX regimen with devimistat are based on clinical practice and literature (e.g., Stein S, et.al, BJC (2016) 114:737-743).*

Day 2:

- Completing the remaining of the 5-FU 42-48-hr infusion starting on Day 1
- Blood sampling for PK (see Sparse PK sampling schedule in Section 7.1.1, Table 13)

Day 3:

- Completing the remaining of the 5-FU 42-48-hr infusion starting on Day 1 and disconnect the 5-FU pump
- Devimistat (may be administered concurrently with 5-FU via a double lumen port)
- Myeloid Growth Factor will be given as per institutional guidelines
- Blood sampling for PK (see Full PK or Sparse PK sampling schedule in Section 7.1.1, Table 12 or Table 13)
- Blood sampling for Cardiac marker (Troponin I [>30 minutes post dosing])
- ECG measurement (see Full ECG or Sparse ECG measurement schedule in Section

7.1.1, Table 14 or Table 15).

Note:

Dosing of agents in the mFFX regimen with devimistat are based on clinical practice and literature (e.g., Stein S, et.al, BJC (2016) 114:737-743).

In the event that time will not permit devimistat administration following 5-FU infusion, devimistat may be administered concurrently with 5-FU via a double lumen port.

FOLFIRINOX Arm 2: FFX

I. Pre-dosing Tests:

- Evaluation of vital signs (including heart rate)*,
- ECOG performance status*,
- Survival*,
- Clinical chemistry*,
- Hematology*,
- Coagulation*,
- NCCN-FACT FSHI-18 questionnaire (if not collected during screening)
- Triphase contrast CT of the chest, abdomen and pelvis **,
- CA19-9**
- ECG (see Sparse ECG measurement schedule in Section 7.1.1, Table 15).
- Blood sampling for Cardiac marker (Troponin I)

II. Oxaliplatin at a dose of 85 mg/m², given as a 2-hr IV infusion

III. Folinic acid at 400 mg/m², given as a 2-hour IV infusion immediately after oxaliplatin

IV. Irinotecan at 180 mg/m², given as a 90-minute IV infusion via a Y-connector

V. concurrently with folinic acid infusion

VI. Fluorouracil (5-FU) at 400 mg/m² as IV bolus, followed by a 42-48-hr continuous IV infusion at 2,400 mg/m², starting immediately after completion of folinic acid and irinotecan

VII. Myeloid Growth Factor will be given as per institutional guidelines.

VIII. Blood sampling for Cardiac marker (Troponin I) post 30 minutes of completion of FFX dose

Note:

**These tests are performed in local labs with results available for review within 24 hrs. before administration of the anti-tumor agents.*

***Performed at the end of every 4th cycle.*

1. **Duration of Treatment:** Treatment will continue for at least 6 months (i.e. a minimum of 12 cycles) in responding patients with acceptable tolerance to therapy (with dose modifications per protocol as needed) unless a criterion for removal from study occurs. Responding patients upon completion of at least 10 cycles and after having two sequential CT scans showing stable disease (no continued decrease in lesion size) will complete 2 additional cycles (to complete a minimum of 12 cycles) of their assigned treatment. Following 12 cycle, and all the subsequent cycles oxaliplatin can be dropped at the discretion of the treating physician if not already omitted. Cycles will continue until one of the criteria for removal from study are reached (see Section 5.3.1).
2. **Observations after the Intervention:** OS will be monitored every 2 months via telephone contact after treatment termination. (Note: During every 2 months post- study treatment telephone contact, information related to cancer treatment received will also be collected).

7.3.3. Treatment Phase

Treatment dosing continues for at least 6 months (i.e. a minimum of 12 cycles) until disease progression (radiological) or a criterion for removal from study are reached. Every cycle will be allowed window of +/- 24 hours.

All patients, on both arms, will complete radiology scans for RECIST evaluation every 8 weeks (+/- 7 days). Radiology will be assessed using triphase contrast CT of the chest, abdomen and pelvis. MRI assessments of tumor status may replace CT scans if needed. Serum levels of tumor marker CA19-9 and performance status also will be assessed every 8 weeks.

Chemotherapy breaks, of 3 weeks or less only, for patient emergencies are allowed and must be

documented.

CYCLE: 2 (Day 15 – Day 29):

1. **Adverse Event Assessment:** record adverse events as reported by participant or observed by investigator
2. **Pre-dosing Tests:** Clinical hematology (including coagulation) and chemistry tests as well as PRO has to be done at this cycle
3. **Administration of Study Treatment:** same as Cycle 1
4. **Sparse PK sampling** (see Sparse PK sampling schedule in Section 7.1.1, Table 13)
5. **Sparse ECG** (see Sparse ECG measurement schedule in Section 7.1.1, Table 15)

CYCLE: 3 (Day 30 – Day 44):

1. **Adverse Event Assessment:** record adverse events as reported by participant or observed by investigator
2. **Pre-dosing Tests:** Clinical hematology (including coagulation) and chemistry tests
3. **Administration of Study Treatment:** same as Cycle 1
4. **Sparse PK sampling** (see Sparse PK sampling schedule in Section 7.1.1, Table 13)
5. **Sparse ECG** (see Sparse ECG measurement schedule in Section 7.1.1, Table 15)

CYCLE: 4 (Day 45 – Day 59):

1. **Adverse Event Assessment:** record adverse events as reported by participant or observed by investigator
2. **Pre-dosing Tests:** Clinical hematology (including coagulation) and chemistry tests as well as PRO has to be done at this cycle
3. **Administration of Study Treatment:** same as Cycle 1
4. **Observations after the Intervention:** radiology scan for the measurement of ORR (approximate, all scans will be done every 8 weeks, +/-7 days), CA19-9, and optional blood draw
5. **Sparse PK sampling** (see Sparse PK sampling schedule in Section 7.1.1, Table 13)

CYCLE: 5 (Day 60 – Day 74):

1. **Adverse Event Assessment:** record adverse events as reported by participant or observed by investigator

2. **Pre-dosing Tests:** Clinical hematology (including coagulation) and chemistry tests
3. **Administration of Study Treatment:** same as Cycle 1
4. **Sparse PK sampling** (see Sparse PK sampling schedule in Section 7.1.1, Table 13)

CYCLE: 6 (Day 75 – Day 89):

1. **Adverse Event Assessment:** record adverse events as reported by participant or observed by investigator
2. **Pre-dosing Tests:** Clinical hematology (including coagulation) and chemistry tests as well as PRO has to be done at this cycle
3. **Administration of Study Treatment:** same as Cycle 1
4. **Sparse PK sampling** (see Sparse PK sampling schedule in Section 7.1.1, Table 13)
5. **Sparse ECG** (see Sparse ECG measurement schedule in Section 7.1.1, Table 15)

CYCLE: 7 (Day 90 – Day 104):

1. **Adverse Event Assessment:** record adverse events as reported by participant or observed by investigator
2. **Pre-dosing Tests:** Clinical hematology (including coagulation) and chemistry tests
3. **Administration of Study Treatment:** same as Cycle 1
4. **Sparse PK sampling** (see Sparse PK sampling schedule in Section 7.1.1, Table 13)

CYCLE: 8 (Day 105 – Day 119):

1. **Adverse Event Assessment:** record adverse events as reported by participant or observed by investigator
2. **Pre-dosing Tests:** Clinical hematology (including coagulation) and chemistry tests as well as PRO has to be done at this cycle
3. **Administration of Study Treatment:** same as Cycle 1
4. **Observations after the Intervention:** radiology scan for the measurement of ORR (approximate, all scans will be done every 8 weeks, +/-7 days), CA19-9 and optional blood draw
5. **Sparse PK sampling** (see Sparse PK sampling schedule in Section 7.1.1, Table 13)

CYCLE: 9 (Day 120 – Day 134):

1. **Adverse Event Assessment:** record adverse events as reported by participant or observed by investigator
2. **Pre-dosing Tests:** Clinical hematology (including coagulation) and chemistry tests
3. **Administration of Study Treatment:** same as Cycle 1
4. **Sparse PK sampling** (see Sparse PK sampling schedule in Section 7.1.1, Table 13)
5. **Sparse ECG** (see Sparse ECG measurement schedule in Section 7.1.1, Table 15)

CYCLE: 10 (Day 135 – Day 149):

1. **Adverse Event Assessment:** record adverse events as reported by participant or observed by investigator
2. **Pre-dosing Tests:** Clinical hematology (including coagulation) and chemistry tests as well as PRO has to be done at this cycle
3. **Administration of Study Treatment:** same as Cycle 1
4. **Sparse PK sampling** (see Sparse PK sampling schedule in Section 7.1.1, Table 13)

CYCLE: 11 (Day 150 – Day 164):

1. **Adverse Event Assessment:** record adverse events as reported by participant or observed by investigator
2. **Pre-dosing Tests:** Clinical hematology (including coagulation) and chemistry tests
3. **Administration of Study Treatment:** same as Cycle 1
4. **Sparse PK sampling** (see Sparse PK sampling schedule in Section 7.1.1, Table 13)

CYCLE: 12 (Day 165 – Day 179):

1. **Adverse Event Assessment:** record adverse events as reported by participant or observed by investigator
2. **Pre-dosing Tests:** Clinical hematology (including coagulation) and chemistry tests as well as PRO has to be done at this cycle
3. **Administration of Study Treatment:** same as cycle 1.
4. **Observations after the Intervention:** radiology scan for the measurement of ORR (approximate, all scans will be done every 8 weeks, +/-7 days), CA19-9 and optional blood draw
5. **Sparse PK sampling on Cycle 12** (see Sparse PK sampling schedule in Section 7.1.1,

Table 13)

6. Sparse ECG (see Sparse ECG measurement schedule in Section 7.1.1, Table 15)

**After the first cycle (Cycle 1)*

All subsequent cycles (beyond Cycle 12), the following assessments should be completed:

- Physical Examinations
- Vital Signs
- Obtain CT scan (or MRI) every 8 weeks
- Blood sample collection for the following tests: Hematology, Blood Chemistry, Coagulation, and CA 19-9 every 4 weeks (or even cycle (eg, Cycle 14, Cycle 16, etc).
- Collect AE and SAE
- Pregnancy test
- Dosing of drug (all the subsequent cycles oxaliplatin can be dropped at the discretion of the treating physician if not already omitted. Cycles will continue until one of the criteria for removal from treatment are reached. (see Section 5.3.1)
- NCCN-FACT FHSI-18 Questionnaire (PRO)

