Cycle 1	Day 1	
Devimistat: IV infusion at the rate of 4 mL/min at the dose of 500 mg/m² concurrently with D5W at the rate of 125mL/hour (2.08mL/min) via a central venous catheter
 
mFFX (given immediately after devimistat administration):
 
 - Oxaliplatin at 65 mg/m² given as a 2-hr IV infusion - Folinic acid at 400 mg/m² given as a 90-min (1.5 hr) infusion immediately after oxaliplatin, and concurrently with Irinotecan at 140 mg/m² given as a 90-min IV infusion via a Y-connector. - Flurouracil (5-FU) at 400 mg/m² as bolus followed by a 42-48-hr infusion at 2,400 mg/m², starting immediately after completion of folinic acid and irinotecan
	Day 2	
mFFX:
 
 - Completing the remaining of the 5-FU 42-48-hr infusion starting on Day 1
	Day 3	
mFFX:
 
 - Completing the remaining of the 5-FU 42-48-hr infusion starting on Day 1, 2 and disconnect the 5-FU pump. 
devimistat:
 
 - Devimistat (500 mg/m²), IV infusion at the rate of 4 mL/min via a central venous catheter after completion of 5-FU infusion. Devimistat infusion must be administered concurrently with D5W at the rate of 125mL/hour (2.08mL/min) via a central venous catheter. In the event that time will not permit devimistat administration following 5-FU infusion, devimistat may be administered concurrently with 5-FU via a double lumen port.
	Day 4 (-/+ 24 hours)	Myeloid Growth factor per institutional guidelines
	Days 5 -14	No treatment
Cycle 2 and subsequent Cycles (every 2 weeks)		Same as Cycle 1

Dosing as above will continue for at least 6 months in responding patients with acceptable tolerance to therapy (with dose modifications per protocol as needed) unless a criterion for removal from study occurs. Responding patients upon completion of at least 10 cycles and after having two sequential CT scans showing stable disease (no continued decrease in lesion size) will complete 2 additional cycles (to complete a minimum of 12 cycles) of their assigned treatment.

Following 12 cycle and all the subsequent cycles oxaliplatin can be dropped at the discretion of the treating physician if not already omitted. Cycles will continue until one of the criteria for removal from study are reached (Section 5.3.1).

FOLFIRINOX (Control Arm 2; FFX):

Calculation of the Amount of FOLFIRINOX for Each Patient:

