6.1.6. Dose Adjustments/Modifications/Delays

No dose modifications are allowed for devimistat in this study.

The dose of Folinic Acid is not modified for any toxicity but is omitted if fluorouracil is omitted. Once a dose of any of the drugs comprising FFX is decreased, re-escalation of the dose is not permitted. Patients are taken off the study if they develop the same Grade 4 toxicity despite dose reduction. The dose adjustment scheme for FFX is dependent on the type of toxicities, as described below.

Hematologic Toxicity

Once hematologic toxicity is observed in a patient, do not retreat the patient with mFFX or FFX until the absolute neutrophil count is $\geq 1.5 \times 10^9/L$ and the platelet count is $\geq 75 \times 10^9/L$. The dose modification schemes for FFX related to hematologic toxicity are shown in Table 9.

Primary prophylaxis with myeloid growth factor will be at the discretion of the treating physician and as per the ASCO guidelines. If the patient is not being treated with myeloid growth factor the initial modification for neutropenia should be the addition of a myeloid growth factor. If the patient is already on a myeloid growth factor, then dose adjustments are as outlined in Table 9.

Table 9 Dose Modifications for Hematological Toxicities on Day 1 of a Cycle. Cycles are Every Two Weeks.

Day 1	Delay the Start of a Treatment Cycle*	Doses Reduction		
		Irinotecan	Oxaliplatin	Fluorouracil (5-FU)
ANC <1.5x10 ⁹ /L	Withhold treatment until granulocytes ≥1.5x10 ⁹ /L.	1 st occurrence: Continue same dose	1 st occurrence: Continue same dose	1 st occurrence: Delete bolus 5-FU
		2 nd occurrence: Reduce to 80% of starting dose	2 nd occurrence: Continue same dose	
		3 rd occurrence: Reduce to 50% of starting dose	3 rd occurrence: Reduce to 80% of starting dose	
		4 th occurrence: Discontinue irinotecan	4 th occurrence: Continue on 80% of starting dose	
Platelets <75x10 ⁹ /L	Withhold treatment until platelets ≥75x10 ⁹ /L.	1 st occurrence: No dose reduction	1 st occurrence: No dose reduction	1 st occurrence: Delete bolus 5-FU
		2 nd occurrence: Reduce to 80% of starting dose	2 nd occurrence: Reduce to 80% of starting dose	
		3 rd occurrence: Reduce to 50% of starting dose	3 rd occurrence: Discontinue oxaliplatin	
		4 th occurrence: Discontinue irinotecan	4 th occurrence: Discontinue oxaliplatin	

Table 10 Dose Adjustments According to Non-Hematological Toxicities (Excluding Alopecia, Nausea and Vomiting).

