7.3.6. Schedule of Events Table

Table 16 Schedule of Events: Experimental Arm

Experimental Arm: devimistat + mFFX								
Assessments	Pre-Study Screen	Cycle 1 (+/- 24 hr.) and Subsequent Cycles (+/- 24 hr.)					End of treatment	Follow-Up Every 2 Months Until Death
		Day 1	Day 2	Day 3	Day 4	Days 5-14		
Informed consent	√							
Medical history	√							
Pregnancy test for women of childbearing Potential (monthly- day 1 of even numbered cycle)	√	√					√	
Hemoglobin A1c (HbA1c)	√							
devimistat administration (dosing)		√		√				

A Phase III Multi-Center Open-Label Randomized Trial to Evaluate Efficacy and Safety of FOLFIRINOX (FFX) versus Combination of CPI-613 with modified FOLFIRINOX (mFFX) in Patients with Metastatic Adenocarcinoma of the Pancreas

Protocol: PANC003

Version 9.0

June 10, 2021

mFOLFIRINOX (mFFX)		√	√	√				
AE and Con. Med. Assessment		AEs and con meds will be assessed at each patient visit						
Myeloid growth factor (as per institutional guidelines)*					√			
Evaluation of symptoms and vital signs ⁷	√	√					√	
ECOG performance status ⁶ and survival	√	√					√	
Clinical chemistry, hematology and coagulation	√	√				√ (day 7 or 8)	√	
Triphase contrast CT of the chest, abdomen and pelvis (or MRI if needed) (every 8 weeks)	√						√ (unless one was performed within the last 14 days)	
Blood sampling for biomarker ¹	√							
CA19-9 (every 8 weeks up to 12 cycles and every 4 weeks beyond 12 cycles)	√	√					√	
Blood sampling for Full PK Analysis ²		√		√				
Blood sampling for Sparse PK Analysis ³		√		√				
Cardiac Marker (Troponin I) ⁸		√		√				
Full ECG ⁴		√		√				
Sparse ECG ⁵		√		√				
Phone contact								√
NCCN-FACT FHSI-18 Questionnaire ⁶	√	√					√	

*Myeloid growth factor can be given at Day 4 or any day at the discretion of the treating physician per ASCO and institutional guidelines

¹ Prior to treatment initiation (within 4 weeks prior to 1st dose) and prior to each restaging scan.

² Full PK analysis will be carried out only for cycle 1. For Full PK sampling schedule see Section 7.1.1, Table 12

³ see Sparse PK sampling schedule in Section 7.1.1, Table 13

⁴ Full ECG measurement will be carried out only for cycle 1. For Full ECG measurement schedule see Section 7.1.1, Table 14

⁵ see Sparse ECG measurement schedule in Section 7.1.1, Table 15

⁶ at baseline and day 1 of every even numbered cycle

⁷ Vital signs include heart rate

⁸ see Cardiac Marker (Troponin I) schedule under Section 7

Table 17 Schedule of Events: Control Arm

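### Protocol Section 7.3.3 can be read as reducing hematology, chemistry and coagulation to every 4 weeks after Cycle 12, which is inconsistent with Section 7.2.1, Tables 16–17 and the Day 1 counts used by Table 9

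*Protocol*

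**What the plan says.** Protocol Section 7.3.3 ends with a list of assessments for all cycles beyond Cycle 12. One bullet reads "Blood sample collection for the following tests: Hematology, Blood Chemistry, Coagulation, and CA 19-9 every 4 weeks (or even cycle", followed by Cycle 14 and Cycle 16 as examples. For Cycles 2 to 12 the same section names hematology with coagulation, and chemistry, as pre-dosing tests in every cycle, odd and even. That line does not recur after Cycle 12; the quoted bullet takes its place.

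Treatment does not slow down. Table 7 gives "Cycle 2 and subsequent Cycles (every 2 weeks") as the pattern, and Table 8 does the same for the control arm. The text after Table 7 says "Following 12 cycle and all the subsequent cycles oxaliplatin can be dropped at the discretion of the treating physician", and cycles go on until a removal criterion is met.

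Three other parts of the protocol bear on the same blood tests:

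- Section 7.2.1: "CBC (complete blood count) and CMP (comprehensive metabolic panel) will be monitored weekly, on Day 1 and Day 7 or 8", for toxicity assessment, with no cycle limit.
- Section 7.3.6, Tables 16 and 17: chemistry, hematology and coagulation are ticked on Day 1 and on Day 7 or 8. In Table 16 the columns are headed "Cycle 1 (+/- 24 hr.) and Subsequent Cycles (+/- 24 hr".). The row that changes after Cycle 12 is "CA19-9 (every 8 weeks up to 12 cycles and every 4 weeks beyond 12 cycles"). SAP Appendix I has the same laboratory row.
- Section 6.1.6: Table 9 is titled "Dose Modifications for Hematological Toxicities on Day 1 of a Cycle. Cycles are Every Two Weeks". The text above it says that after hematologic toxicity sites should "do not retreat the patient with mFFX or FFX until the absolute neutrophil count is" back at its threshold, with a platelet threshold as well.

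**The concern.** The delay and reduction rules for irinotecan, oxaliplatin and 5-FU in Table 9 need a neutrophil and platelet count on Day 1 of each cycle. Table 10 likewise uses bilirubin to decide on irinotecan. If a coordinator takes the list for cycles beyond 12 as the specific instruction that governs from Cycle 13 onward, no count is scheduled in the odd-numbered cycles, although chemotherapy is given in them. The Day 7 or 8 check drops out as well.

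Table 9 also escalates by occurrence, from first to fourth. A low count in an odd cycle that nobody draws is neither acted on nor counted toward the next step. The stake is patient safety in late cycles, and uniform conduct between sites that work from different pages of the same protocol.

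**Working it through.** No sample size, power or alpha figure is involved, and the plan states no figure to reproduce. The check is a comparison of the texts plus a count of scheduled draws.

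**Inputs**

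- Cycle length: 14 days, before and after Cycle 12 (Tables 7 and 8).
- Schedule A, Section 7.3.3 read literally: one draw per even-numbered cycle.
- Schedule B, Section 7.2.1 and Tables 16–17: two draws per cycle, on Day 1 and on Day 7 or 8.
- Illustrative window: Cycles 13 to 24, which is 12 × 14 = 168 days, or 24 weeks.

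**Draws per 28 days**

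- Schedule A: 28 / 28 = 1.
- Schedule B: 2 cycles × 2 draws = 4.
- Ratio 4 / 1 = 4, so A has 1 − 1/4 = 75% fewer scheduled draws than B.

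**Draws in Cycles 13 to 24**

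| | Schedule A | Schedule B |
|---|---|---|
| Day 1 draws | 6 (Cycles 14, 16, 18, 20, 22, 24) | 12 |
| Day 7 or 8 draws | 0 | 12 |
| Total | 6 | 24 |
| Cycles with no scheduled Day 1 count | 6 (Cycles 13, 15, 17, 19, 21, 23) | 0 |

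**Which tests conflict**

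- CA19-9: no conflict. Section 7.3.3 and Tables 16–17 both give 4-weekly beyond Cycle 12.
- Hematology and chemistry: the literal reading of 7.3.3 conflicts with 7.2.1, with Tables 16–17, and with what Table 9 needs.
- Coagulation: it conflicts with Tables 16–17 only, because the weekly note in 7.2.1 covers the blood count and metabolic panel.

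**Can Table 9 be applied?** Its rows are triggered by Day 1 neutrophils and platelets, and neither its title nor its rows carry a cycle limit. Under Schedule B the input is scheduled in all 12 cycles. Under Schedule A it is scheduled in 6 of 12. The retreatment rule in Section 6.1.6 would lead to repeat counts once a toxicity has been seen, but it does not create a count in an odd cycle in which none was drawn.

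**The case against.** The strongest reply is that the protocol already requires the counts. Section 7.2.1, both schedule tables and the SAP appendix ask for them with no stop at Cycle 12, and Table 9 presupposes them. The 7.3.3 bullet is also ambiguous: the interval stands directly after CA19-9, and Table 16 ties the 4-weekly interval beyond Cycle 12 to CA19-9 alone. On that reading everything agrees, with safety tests each cycle and CA19-9 every second cycle.

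Much of this stands, and it rules out three stronger conclusions that a reader might draw.

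- **That every odd cycle after Cycle 12 is dosed without counts.** The documents do not say so. It follows only for a site that reads the bullet broadly and also sets aside 7.2.1 and the schedule tables.
- **That the two schedules are mutually exclusive.** They are not. Section 7.3.3 does not forbid extra draws, and a site that samples on Day 1 and Day 7 or 8 of every cycle also has its even-cycle samples.
- **That the grade 3/4 safety outcome is biased, or that a given number of patients is affected.** Protocol Section 9.4.4 counts patients with at least one such event, so after Cycle 12 only first-ever events matter. The documents give neither the number of patients still on treatment at Cycle 13 nor how sites read the bullet, so no size can be attached to either claim.

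The reply does not remove the problem. The bullet is one list with one interval at its end, the example cycles are even, and the every-cycle pre-dosing line used up to Cycle 12 is gone. A careful reader can reasonably take the interval to cover all four tests.

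**Conclusion.** The point holds as an internal contradiction about safety laboratory tests after Cycle 12. Its size depends on which section a site follows: 1 scheduled draw per 28 days under a literal 7.3.3, against 4 under Section 7.2.1 and Tables 16–17. Under the former, half of the late cycles have no scheduled Day 1 count for Table 9; under the latter, none lack it.

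This rests on the 14-day cycle continuing after Cycle 12, which the protocol states, and on the broad reading of the bullet, which is natural but not the only one. Nothing in the documents shows a deliberate decision to reduce monitoring, so it should not be described as a design choice. No view is taken here on which frequency is right.

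**What to change.** Reconcile Protocol Section 7.3.3 (cycles beyond 12) with Section 7.2.1, Tables 16 and 17, and Table 9. Split the bullet in two: one line for CA19-9, and one for hematology, chemistry and coagulation, each with its own interval. Give the same intervals in every place, SAP Appendix I included, and check that Table 9 can be applied in each cycle under whatever schedule is stated. The sponsor's clinical team decides that schedule.

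The cost is one bullet in a protocol amendment, matching edits where needed, and a letter to sites. Any sampling cost depends on the schedule chosen; Day 1 draws fall on visits at which the patient already attends for dosing.
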